5.1 Missing values

In all analyses, missing values on either the outcome measures or on the covariates will be handled by using multiple imputation by chained equation (MICE) with $m = 30$ imputed datasets if MAR or MCAR assumption holds. To evaluate whether individual missings are MAR, MCAR or MNAR we will use information on reasons of missings or drop out (e.g. if patients drop out due to worsening of health status or not). In case of death, no imputation will be implemented for the time afterwards.

6 Sample size

Due to the exploratory nature of the trial, a formal sample size calculation is not applicable [23]. The trial has two subgroup strata (I) sex (male/female); (II) condition of the skin (no IAD vs. IAD Category 1A) and three treatment arms. Based on these conditions and following the recommendations for exploratory trials [36], a sample size of $n = 60$ participants per treatment group is considered feasible and sufficient to describe group differences. In order to compensate a possible loss-to-follow-up, $n = 70$ patients per group will be included.

7 Statistical analyses / methods

For all analyses, appropriate descriptive statistics (mean, standard deviation, median, interquartile range, absolute and relative frequencies) depending on the scale and distribution of the outcome variable for each time point will be presented. For relative frequencies of outcome variables, their cumulative incidences will be reported as well. Sensitivity analyses include per protocol analyses and complete case analyses in the ITT (without imputation).

7.1 Demography and baseline characteristics

Demography and baseline characteristics will be presented descriptively without any comparisons. Depending on the distribution either mean or median will be reported with standard deviation or interquartile range respectively.

7.2 Analyses of endpoints

Because of the exploratory nature of the trial and according to methodological guidance for exploratory trials, a distinction between primary and secondary endpoints is not made [23]. Because the main aim is to prevent IAD, IAD incidence is likely to be considered as a primary outcome in a possible subsequent confirmatory trial and is therefore considered as primary efficacy variable.

For all outcomes, total group differences are reported by the corresponding effect size based on the statistical models as outlines below and corresponding 95% confidence intervals. Relevant timepoints will be Day 6 and Day14. Day0 reports will be presented as is.

The relevant blinded group comparisons are: A vs. B; A vs. C; B vs. C.

For cumulative incidence rates of IAD, Kaplan-Meier Curves will be presented with time ranging from inclusion to IAD onset, i.e. the first occurrence of IAD 2A or 2B. Censoring occurs if patients withdraw from the study before the onset of an IAD or if the study is terminated before IAD onset. Mixed effects Cox regression model (shared frailty model) will be carried out for group comparisons of incidence rates. The latter includes group allocation, sex, setting (nursery home, geriatric hospital ward) and time (continuous) as fixed effects and random intercepts for the ward and the patients. The resulting Hazard ratios for IAD will be presented. Potential non-linear time effects will be explored and modelled using fractional polynomials or splines.

Group differences for categorical, dichotomous responses are calculated by estimating group effects from either generalized linear mixed-effects models (binary logistic) - including particular baseline status (maceration, IAD-related itch), group allocation, sex, setting and time as fixed effects and random intercepts per ward and patients - or nonparametric analysis of longitudinal data depending on the distribution of the data. For the Erosion model, no baseline adjustment is considered due to its presence is an exclusion criterion.

List:

- Erosion (no/ yes)
- Maceration (no/ yes)
- IAD related itch (no/ yes) [only measured if IAD present]
- IAD-related pain (no/yes) [only measured if IAD present]

Group differences for numerical, ordinal responses are calculated by estimating group effects from either cumulative link mixed-effects (ordinal) - adjusted for baseline status, group allocation, sex, setting and time as fixed effects and random intercept per ward-ID and patient as random effects - or nonparametric analysis of longitudinal data depending on the distribution of the data.

In case of non-occurrence of one category, the model will reduce to a generalized linear mixed-effects models (binary logistic) as stated above.

List:

- Erythema (none/pink/red or bright red)

Group differences for numeric, interval scaled responses are calculated by estimating group effects from either linear mixed-effects models - adjusted for baseline status, group allocation, sex, setting and time as fixed effects and random intercept per ward and patient as random effects - or nonparametric analysis of longitudinal data depending on the distribution of the data.

List:

- Erythema (total) level (in arbitrary units (AU) from 0 to 999)
- IAD related pain (numeric rating scale from 0 to 10) [for IAD present]
- Patient satisfaction (numeric rating scale from 0 to 10) [both: for MMSE ≥ 24 and above]

In case of nonlinear relationship, nonlinear mixed-effects models will be considered. The check will occur visually by scatterplots.

The distribution of outcome variables will be checked by raincloud plots (boxplot + histogram).

No adjustment for multiple comparisons will be made and results are bound to be seen exploratory.

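### The SAP names Day 6 and Day 14 for its model-based group differences, but the mixed models as written give one time-averaged contrast, the same on both days

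*Combined protocol and SAP*

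**What the plan says.** SAP 7.2 states, for every outcome, that "total group differences are reported by the corresponding effect size based on the statistical models as outlines below and corresponding 95% confidence intervals". The next sentence is "Relevant timepoints will be Day 6 and Day14". The models then follow:

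- **Binary outcomes** (erosion, maceration, itch, pain yes/no): logistic mixed model with "group allocation, sex, setting and time as fixed effects and random intercepts per ward and patients", plus baseline status except for erosion.
- **Visual erythema** (ordinal): cumulative link mixed model "adjusted for baseline status, group allocation, sex, setting and time as fixed effects and random intercept per ward-ID and patient as random effects".
- **Mexameter erythema, pain score, satisfaction**: linear mixed model "adjusted for baseline status, group allocation, sex, setting and time as fixed effects and random intercept per ward and patient as random effects".
- **IAD incidence**: Kaplan-Meier curves and a shared-frailty Cox model. Of the Cox model the SAP says "The latter includes group allocation, sex, setting (nursery home, geriatric hospital ward) and time (continuous) as fixed effects", and then "Potential non-linear time effects will be explored and modelled using fractional polynomials or splines".

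Each mixed model has as its alternative a "nonparametric analysis of longitudinal data depending on the distribution of the data", with no factors or effect measure stated. The only interactions in the SAP are those of subgroup by intervention group in 7.3. The shell for secondary outcomes in 10.2 (Table 3) has one row per contrast and no timepoint column.

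**The concern.** The SAP singles out two days but specifies models in which the arm effect cannot differ between days. If contrasts are read out at Day 6 and Day 14, the report will show matching pairs of estimates, and a reader could take this for evidence of a stable effect. It would only be a consequence of the model.

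The trial's primary objective includes estimating effect sizes for a later confirmatory trial (SAP 1.1.1). If a protectant's effect builds up or wanes over the 14 days, the adjusted effect size passed on for planning is an average over follow-up and not the effect at the end of treatment.

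**Working it through.** The plan gives no figure to reproduce here, since it has no formal sample size calculation. The check is one of model structure, followed by an illustration of size.

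**1. Structure.** Write each mixed model as

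g(E[Y]) = b0 + b_arm + f(t) + covariates + random intercepts.

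The A–C contrast at day t is [b_A + f(t)] − [b_C + f(t)] = b_A − b_C. The time term cancels whatever the form of f: linear, quadratic, spline or categorical. The standard error is that of b_A − b_C, so the interval is also the same on every day. A flexible time main effect does not change this. Only a term that lets time act differently by arm does.

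**2. Check on simulated data.** All data values are assumed: 210 patients, three arms, visits on Days 2 to 14, and an arm effect that grows with time (true A–C of −36 AU at Day 6 and −84 AU at Day 14). The logistic fit was a GEE clustered on patient, standing in for the logistic mixed model.

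| Model | Day 6 | Day 14 |
|---|---|---|
| Linear mixed, arm + time | −59.442 | −59.442 |
| Same, plus quadratic time | −59.442 | −59.442 |
| Linear mixed, arm × time | −48.1 | −93.4 |
| Logistic OR, arm + time | 0.549 | 0.549 |
| Logistic OR, arm × time | 0.746 | 0.305 |

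The identity is specific to the scale. In the same additive logistic fit the risk difference is −0.070 at Day 6 and −0.101 at Day 14. Cohen's d could also differ by day if it were standardised by a day-specific SD, but its numerator would not.

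**3. Size of the averaging.** Assume a log odds ratio that is linear in time from 0 at Day 0 to log 0.40 at Day 14, with the seven follow-up visits weighted equally.

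- Mean of d/14 over d = 2, 4, …, 14 is 8/14, so the reported OR is 0.40^(8/14) = 0.59 on both days.
- Under the assumed trajectory the OR at Day 6 is 0.40^(6/14) = 0.68, and at Day 14 it is 0.40.

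Assume instead that the effect wanes from 0.40 at Day 2 to 1.0 at Day 14.

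- The reported OR is 0.40^(1/2) = 0.63 on both days.
- Under that trajectory the OR at Day 6 is 0.40^(8/12) = 0.54, and at Day 14 it is 1.0.

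A logistic fit weights visits by information, not equally. Fitting arm plus time to expected data without random effects, under assumed control prevalences (flat 10%; rising 2–20% or 5–35%; falling 20–5%), gives 0.53 to 0.67 for the growing effect and 0.58 to 0.76 for the waning one.

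**4. IAD incidence.** A Cox model without a time-varying effect gives one hazard ratio for all days, but cumulative incidence still separates by day. With an assumed hazard ratio of 0.5, a constant hazard and an assumed control incidence at Day 14 of c, the control hazard is h = −ln(1 − c)/14, and the difference at day d is exp(−h·d) − exp(−0.5·h·d). For c = 10%, 20% and 35% this is −2.2, −4.4 and −8.0 percentage points at Day 6, and −4.9, −9.4 and −15.6 at Day 14. Day-specific results for this outcome can therefore come from the planned Kaplan-Meier analysis.

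**5. Parameter count for the fix.** Two arm terms times six visit terms (seven follow-up visits) give 12. If time would otherwise have been linear, categorical visit also adds 6 − 1 = 5 main-effect terms, so 17 in all. With linear time the interaction costs 2 × 1 = 2.

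**The case against.** The strongest reply is that the SAP never says the model contrasts will be evaluated on each of the two days. It speaks of total group differences, and the results shell has no timepoint, which fits a single overall effect. That reading is possible, and a time-averaged contrast is a legitimate quantity in a small trial. But the sentence on Day 6 and Day 14 then has no meaning for the models it introduces, and the SAP does not say what else it governs. Either way the text needs repair.

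The SAP also allows nonparametric and nonlinear alternatives. These depend on checks of the data, and neither is stated to include an arm-by-time term. They leave the question open.

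Three other objections stand and limit the point:

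- A reader might infer that a changing effect would go unseen. The documents do not support that. SAP 7 requires descriptive statistics at each timepoint, protocol 4.3 plans mean differences between groups and time points and confidence intervals for between-group differences, and Kaplan-Meier curves are planned.
- A reader might infer that the planning input for the likely confirmatory primary outcome is lost. It is not. IAD incidence has Kaplan-Meier estimates at any day; the mixed models serve outcomes that SAP 4.3 calls secondary.
- A reader might take 0.59 as what the model would report. It rests on an assumed trajectory and equal weights, and the documents give neither a trajectory nor outcome frequencies.

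It is also fair that categorical visit by arm is fragile for itch and pain, which are measured only when IAD is present, and for pain scores on the numeric scale and satisfaction, which need an MMSE of at least 24 (SAP 4.4).

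**Conclusion.** The point holds for the binary, ordinal and linear mixed models as written, on the odds ratio, cumulative odds ratio and mean difference scales: one time-averaged contrast, with the same value and interval at Day 6 and Day 14. This follows from the model form and needs no assumption about the data. It does not extend to risk differences, Kaplan-Meier estimates or per-visit descriptive results, and the documents do not show what the nonparametric alternative would give.

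The size is illustrative. With the assumed growing effect, an odds ratio of roughly 0.6 (0.53 to 0.67 over the prevalences tried) would stand for both days, against 0.68 and 0.40.

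Severity is should-fix. The trial is exploratory, SAP 7.2.1 rules out confirmatory tests, and error control is not affected. What is affected is which adjusted effect size is carried forward.

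**What to change.** In SAP 7.2, add an arm-by-time term to the mixed models and estimate A–B, A–C and B–C with 95% confidence intervals at Day 6 and Day 14 from it.

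- **Categorical visit** for outcomes measured in all patients with enough events: Mexameter erythema, visual erythema, maceration.
- **Arm by linear time** for erosion and for outcomes measured only in subsets: itch, pain, satisfaction.
- **IAD incidence:** report Kaplan-Meier cumulative-incidence differences with 95% confidence intervals at both days beside the single hazard ratio.
- **Time-averaged effect:** keep it as a labelled extra.
- **Shell in 10.2:** add a timepoint column.
- **Where an interaction model cannot be fitted:** state that the effect is a time average and that Day 6 and Day 14 apply to the descriptive results only.

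The cost is SAP wording and code. No new data are needed. The statistical price is 2 extra parameters per model with linear time, 12 with categorical visit (17 if time would otherwise be linear), and wider intervals at single days than for the average. Linear time also assumes a straight-line change in the arm effect on the model scale.

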2.2 Application

The primary efficacy analysis will be done using the FAS including estimated values from multiple imputations for missing values (ITT framework). Participants that die, discontinue participation or leave the institution during the study period will be analyzed until that time point (early termination).

An additional analysis of the primary efficacy variable in the PP analysis set will be used as sensitivity analysis. The safety analysis includes calculation of frequencies and rates of adverse and serious adverse events in the safety analysis set.

As the ITT analysis is intended to preserve the original randomization and to avoid potential bias due to exclusion, the PP analysis aims to analyze the possible effects of the intervention administered under optimal conditions. Therefore, both analyzes are a necessary component to determine the feasibility of the applied procedures as well as possible effects of the intervention. Especially with regard to planning of a subsequent confirmatory trial

[figure not shown]
3 Trial centres

The study was conducted in geriatric hospitals/geriatric wards (acute care setting) of participating hospitals and in institutional long-term care facilities (nursing home setting) of the federal state of Berlin, Germany with a recruitment of n = 220 patients. Of these, 25 subjects were enrolled from acute care settings (14 EGZB; 11 Charité-ITS) and 195 subjects were recruited across 18 different nursing homes.

Nr	Participating ward	Number of patients (n)
Geriatric hospitals		
1	EGZB	14
2	Charité intern ITS	11
Nursing homes		
1	NH-01	11
2	NH-02	19
3	NH-03	5
4	NH-04	19
5	NH-05	17
6	NH-06	10
7	NH-07	6
8	NH-08	9
9	NH-09	7
10	NH-10	19
11	NH-11	4
12	NH-12	25
13	NH-13	8
14	NH-14	7
15	NH-15	3
16	NH-16	3
17	NH-17	13
18	NH-18	10

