4.4 Efficacy

The main efficacy variable is the IAD cumulative incidence measured by IAD presence on each visit day (Day0, Day2, ..., Day14). Secondary efficacy variables are Erythema and Maceration level, IAD itch and pain level and patient satisfaction.

- IAD-related itch and pain level (numeric rating scale) are measured at each visit day (Day0, Day2, ..., Day14) if IAD is present and if MMSE \geq 24.
- IAD itch and pain level (PAINAD-G) are measured at each visit day (Day0, Day2, ..., Day14) if IAD is present and if MMSE < 24.
- Patient satisfaction is measured at each visit day (Day0, Day2, ..., Day14) if MMSE \geq 24
- Erythema and Maceration level are measured at each visit day (Day0, Day2, ..., Day14).

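### SAP 7.2 does not say how death before IAD enters the Kaplan-Meier estimate of cumulative incidence; censoring at death would overstate absolute incidence per arm slightly

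*Combined protocol and SAP*

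**What the plan says.** SAP 4.4 sets the main outcome: "The main efficacy variable is the IAD cumulative incidence measured by IAD presence on each visit day". SAP 7.2 assigns the estimator: "For cumulative incidence rates of IAD, Kaplan-Meier Curves will be presented with time ranging from inclusion to IAD onset", with onset defined as "i.e. the first occurrence of IAD 2A or 2B". The censoring rule in the same section reads: "Censoring occurs if patients withdraw from the study before the onset of an IAD or if the study is terminated before IAD onset". Death is not mentioned there. Protocol 4.3 has the same rule and is also silent on death.

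Death appears in two other places. SAP 2.2, on how the analysis sets are applied, says: "Participants that die, discontinue participation or leave the institution during the study period will be analyzed until that time point". SAP 5.1 adds: "In case of death, no imputation will be implemented for the time afterwards".

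Arms are compared by a mixed-effects Cox model that yields hazard ratios (SAP 7.2 and the hazard-ratio table layout in 10.2). SAP 7.3 adds a second time-to-event analysis, with IAD of any category as the event, in participants free of IAD at baseline. Neither document mentions competing risks or a cumulative incidence function.

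**The concern.** Kaplan-Meier treats a censored participant as someone who remains at risk and would have developed IAD at the same rate as those still observed. That can be defended for a resident who moves away. It is not true of one who has died. With deaths censored, one minus Kaplan-Meier estimates the IAD risk in a hypothetical population in which nobody dies, and it cannot fall below the proportion who actually develop IAD.

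The absolute incidence per arm matters because the primary objective is to supply effect sizes for a possible confirmatory trial, and a hazard ratio alone does not size such a trial. Deaths are foreseeable. Participants are at least 65 and incontinent of urine and stool, the SAP provides for death twice, and 25 of the 220 recruited came from acute care (SAP section 3). Excluding people at the end of life lowers the rate but does not guarantee zero.

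**Working it through.** **No figure to reproduce.** The documents give no expected IAD incidence, mortality or event count, and no formal sample size calculation. The rates below are assumptions shown as ranges.

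**Inputs from the documents.** Follow-up is 14 days. The planned size is 70 per arm. The 35.4% prevalence of any IAD in the background section serves only as an upper scenario for 14-day incidence.

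**Assumed.** The 14-day IAD risk without death (what one minus Kaplan-Meier estimates) is I = 10%, 20% or 35.4%. The 14-day mortality is d = 0, 1%, 2% or 5%. Hazards are constant.

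**Formulas.** Over 14 days let L = -ln(1 - I) and M = -ln(1 - d).
- One minus Kaplan-Meier with deaths censored: 1 - exp(-L) = I.
- Actual cumulative incidence (Aalen-Johansen): L/(L + M) × [1 - exp(-(L + M))].

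**Worked case, I = 20%, d = 5%.** L = 0.2231 and M = 0.0513, so L/(L + M) = 0.8131. Also 1 - 0.80 × 0.95 = 0.24. The product is 19.51%, an excess of 0.49 points.

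Excess of one minus Kaplan-Meier, in percentage points, beside the 95% half-width for one arm, 1.96 × √[I(1 - I)/70]:

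| I | d = 0 | d = 1% | d = 2% | d = 5% | Half-width |
|---|---|---|---|---|---|
| 10% | 0 | 0.05 | 0.10 | 0.25 | 7.0 |
| 20% | 0 | 0.10 | 0.19 | 0.49 | 9.4 |
| 35.4% | 0 | 0.16 | 0.33 | 0.83 | 11.2 |

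At 20% incidence the Aalen-Johansen values are 20.00%, 19.90%, 19.81% and 19.51%.

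**Arm difference.** Take 20% against 10%, so that Kaplan-Meier shows 10.0 points.
- Equal mortality of 1%: 19.90 - 9.95 = 9.95 points.
- Equal mortality of 5%: 19.51 - 9.75 = 9.76 points.
- 5% deaths in the higher-risk arm and 1% in the other: 9.56 points.
- 1% and 5% respectively: 10.15 points.

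So Kaplan-Meier overstates the difference in the first three cases and understates it in the last. The half-width for this difference with 70 per arm is 1.96 × √(0.16/70 + 0.09/70) = 11.7 points.

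**Hazard ratio.** The true cause-specific value for 10% against 20% is ln(0.9)/ln(0.8) = 0.472. In 200 simulated trials per scenario (700 per arm to limit small-sample noise, ordinary Cox model without frailty terms, deaths censored), the average was 0.477, 0.473, 0.471 and 0.471 at 0, 2%, 5% and 14.3% deaths. Censoring deaths does not bias it.

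**The case against.** The case against has several parts.

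- **Censoring at death is inferred.** SAP 7.2 never states it. That is true, but SAP 2.2 leaves no other natural reading, and if another was meant, 7.2 still has no rule for death.
- **Kaplan-Meier is not the only incidence estimate.** Protocol 4.3 reports the cumulative incidence as a proportion and offers the curves in addition. SAP 4.2 gives counts and percentages, and SAP section 7 promises cumulative incidences for relative frequencies. A crude proportion does not assume that the dead would have developed IAD. A reader might infer that the trial's main efficacy number is systematically overstated. The documents do not support that: the curve is one of several displays, the arm comparison is the unaffected hazard ratio, and the excess exists only if deaths precede IAD. What remains is that SAP 7.2 assigns Kaplan-Meier to cumulative incidence, so a proportion and a curve could be printed side by side and disagree.
- **A later trial would not be undersized in any meaningful way.** A reader might infer that it would be. Take halving a risk p at two-sided 5% and 80% power: n = 7.849 × [p(1 - p) + (p/2)(1 - p/2)]/(p/2)². This gives 196 per arm at 20%, and 199 to 202 at the Aalen-Johansen values for 2% to 5% deaths. The confidence interval around 20% (10.6% to 29.4%) alone moves the answer from about 404 to 121. The argument also needs equal mortality across arms.
- **SAP 5.1 and 2.2 do not conflict.** Declining to impute after death is compatible with ending follow-up at death. SAP 5.1 shows only that the plan already treats death as different from other missing data.

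**Conclusion.** The point holds as a minor gap. SAP 7.2 should state how death before IAD is handled, and if deaths are censored, one minus Kaplan-Meier is the wrong estimator of the actual risk of IAD. The excess at 20% incidence is 0.1 to 0.5 points for 1% to 5% deaths, roughly 1% to 5% of the confidence half-width for one arm, and zero without deaths. These sizes rest on assumed incidence and mortality and on constant hazards. The direction of the per-arm excess does not depend on the assumed rates. The direction for the difference between arms does depend on how mortality compares across them. The Cox comparison needs no change beyond its label.

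**What to change.** In SAP 7.2, and in the 7.3 analysis of participants without initial IAD:

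1. State that death before IAD is a competing event.
2. Report the Aalen-Johansen cumulative incidence per arm, with 95% confidence intervals at Day 6 and Day 14 (the time points that 7.2 already names), in place of one minus Kaplan-Meier.
3. Keep the Cox model and call its hazard ratio cause-specific.
4. List deaths per arm beside the curves.

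The cost is a few sentences and a standard estimator. SAP 4.1 already lists a termination date and reasons for early termination, some with free text. It shows no separate code for death, so the team should confirm that deaths can be identified from those fields. If nobody dies before IAD, the two estimators coincide and nothing is lost.
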